MUMC+ Maastricht University Medical Center+

NA Non-Applicable

NCGS Non-coeliac gluten sensitivity
NCWS Non-coeliac wheat sensitivity

NSAIDs Nonsteroidal anti-inflammatory drugs

PANAS Positive and Negative Affective Schedule

PIF Participant Information Sheet (in Dutch: "Proefpersoon informatie

formulier")

(S)AE (Serious) Adverse Event

Sponsor The sponsor is the party that commissions the organisation or

performance of the research, for example a pharmaceutical

company, academic hospital, scientific organisation or

investigator. A party that provides funding for a study but does not commission it is not regarded as the sponsor, but referred to

as a subsidising party.

SUSAR Suspected Unexpected Serious Adverse Reaction

VAS Visual Analogue Scale

WMO Medical Research Involving Human Subjects Act (in Dutch: Wet

Medisch-wetenschappelijk Onderzoek met Mensen

WUR Wageningen University & Research

SUMMARY

Rationale: Although wheat- and gluten-containing food products are generally considered to be healthy, a large number of individuals in the general population reduce or limit their intake because of possible symptoms as can be read in the social media and popular books. Some individuals may be prone to developing non-coeliac gluten sensitivity (NCGS) which is accompanied by a range of gastrointestinal (GI) (e.g. abdominal discomfort, bloating, diarrhoea, rumbling, pain) and/or extra-intestinal complaints (e.g. headache, lethargy, depression, anxiety) soon after consuming wheat or gluten, which improve after gluten/wheat withdrawal (14). Evidence for a biological rationale is however limited. Increasing evidence indicates that the expectation that a person may suffer from NCGS may also be fuelled by psychosocial factors, in part by articles in the lay press and social media. Psychological factors and expectation mediate placebo and nocebo effects by influencing GI sensory and motor functions along the bidirectional brain-gut axis. However, few studies have examined the contribution of a negative expectation leading to symptoms when consuming gluten. Therefore, we aim to examine, in a placebo-controlled randomized study, whether expectancy of consuming gluten will impact overall GI symptoms in individuals with NCGS. We hypothesize that expected gluten intake via bread (as influenced by verbal information), but not the actual bread composition (containing gluten or not) affects subjective GI and extra-intestinal symptoms in individuals with NCGS.

Objective: The primary objective of this study is to investigate the effects of consumer expectancy, related to either gluten-containing or gluten-free oat bread, on short-term (within 8 hours) overall symptoms in individuals with NCGS. Secondary objectives include the effects of the actual intake of gluten on overall symptoms and the effect of expected gluten intake and actual gluten intake on individual GI and extra-intestinal symptoms as well as the impact of psychological factors on overall, intestinal and extra-intestinal symptoms after expected or actual gluten intake in individuals with NCGS.

Study design: The study conforms to a randomized, double-blind, controlled intervention study.

Study population: People in the general population with NCGS, aged between 18-70 years old, will be recruited to participate in this study.

Intervention: Participants will first be randomized into two different 'expectancy' groups; either being told that they have to consume "gluten-free" (E-), "gluten-containing" (E+) oat bread for breakfast and lunch. In fact, each expectancy group will be divided into 2 groups that receive either gluten-free (G-) or gluten-containing (G+) oat bread as the actual intervention for breakfast and lunch during the test day. This will lead to 4 groups:

1. Participants with the expectation of receiving gluten-free bread but actually receiving gluten-containing oat bread during the test day. (E-, G+)

- 2. Participants with the expectation of receiving gluten-free bread and actually receiving gluten-free oat bread during the test day. (E-, G-)
- 3. Participants with the expectation of receiving gluten-containing bread and actually receiving gluten-containing oat bread during the test day. (E+, G+)
- 4. Participants with the expectation of receiving gluten-containing bread, but actually receiving gluten-free oat bread during the test day. (E+, G-)

Main study parameters/endpoints: The main study parameter is overall GI symptom score, measured by a 100-mm visual analogue scale (VAS). Secondary study parameters are individual intestinal symptoms (*i.e.* abdominal pain, abdominal discomfort, belching, bloating, flatulence, diarrhoea, constipation, nausea, and urge to empty bowel and fullness) and extraintestinal symptoms (*i.e.* tiredness, headache, foggy mind) measured on a 100-mm VAS. Average stool frequency and consistency will be measured by the Bristol Stool Scale (BSS) before and after intervention. Changes in mood will be measured by Positive and Negative Affect Schedule (PANAS) questionnaire.

Nature and extent of the burden and risks associated with participation, benefit and group relatedness: Participants may experience some burden during this study. Study participants will be required to visit the nearest study site on two separate occasions; a 1-hour screening visit and one test day visit which takes almost the entire day (from 8.00AM – 4.30PM) for the bread (i.e. gluten-free or gluten-containing) intervention. The study oat breads are commercially available in supermarkets in the Netherlands. Bread itself is considered to be a harmless food product, consumed on a daily basis by the general population worldwide. The participants may or may not experience mild GI symptoms after the consumption of the study bread, since the included participants suffer from self-reported gluten sensitivity. Such symptoms typically improve or disappear shortly (mostly within hours) after gluten is withdrawn from the diet. During the test day, participants will be asked to report their GI symptoms, extraintestinal symptoms, stool characteristics every hour. They will also be asked to complete these self-assessments at the end of the test day and at the end of the next 2 days (which takes about 5 minutes in total each day). Moreover, in a subgroup of participants (i.e. those who have not previously been tested for coeliac disease, and who still consume a low level of gluten in their diet) a blood sample will be taken (by venepuncture) to exclude coeliac disease by means of serological tests on anti-tTG IgA. This requires participants to make an additional 20-minute visit to the nearest study site prior to the screening visit, may lead to minor discomfort and can cause small and transitory hematoma/bruises to appear.

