3. STUDY DESIGN

The negative expectancy of consuming gluten on overall symptoms in individuals with NCGS will be investigated in a multicentre, randomized, double-blind, controlled intervention study. Participants will first be randomized into a group told that they will receive gluten-containing bread (E+) or gluten-free oat bread (E-). Subsequently, within each arm, participants will be randomized to gluten-containing oat bread (G+) or gluten-free oat bread (G-), which they will receive during the test day (see also Figure 2). An intervention of 1-day has been chosen as most symptoms develop within 6 hours in 72% of NCGS subjects (see also inclusion criteria) (14). In this respect, an 8 hours follow-up is sufficient to pick up changes in acute overall symptoms and to keep the study protocol feasible for participants. Additionally, the risk of a single consumption of gluten-containing bread for breakfast and lunch is negligible. Moreover, longer treatment periods would increase the burden for the participants and might lead to higher non-adherence rates. Nonetheless, a follow-up period of 2 days is included to monitor the effects of the 1-day bread intervention and the disappearance of the symptoms during these days.

[figure not shown]

Figure 2. Study design. (E- = Expectancy of getting gluten-free bread, E+ = Expectancy of getting gluten-containing bread, G+ = actual gluten-containing bread, G- = actual gluten-free bread).

Participant recruitment will start after the Medical Research Ethics Committee (METC) of Maastricht University Medical Center+ (MUMC+) has approved the study according to the revised version of the Guidelines of the Declaration of Helsinki (64th WMA General Assembly, Fortaleza, Brazil, October 2013). The study will be executed according to International Conference on Harmonisation (ICH) and Good Clinical Practice (GCP) guidelines.

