 - a. Coeliac disease test (at MUMC+, Amsterdam UMC or WUR)
- 2. Test day Day 1 (at MUMC+, Amsterdam UMC, WUR or otherwise (in consultation))
 - a. Randomization and treatment allocation
- 3. Follow-up questionnaires End of day 1, day 2 and 3
- 4. Debriefing (by mail), when all 80 participants have completed the study.

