3.1 Screening visit

A screening visit will be performed to assess the eligibility of the volunteers to participate in this study. First, in- and exclusion criteria will be checked. Participants must have an overall symptom score for gastro-intestinal symptoms below or equal to 30mm in VAS-score over the last week (see "F1.1_Screeningsvragenlijst_WoWstudy_Versie1.1_04-04-2018") in order to participate in this study, after a gluten-free or gluten-restricted diet for at least one week. Thereafter, several baseline parameters will be assessed by means of questionnaires to obtain information about general health (e.g. personal history of medical and psychiatric illness (e.g. pregnancy), lifestyle, weight and height, adherence to gluten-free diet and general health (see paragraph 7.3)).

Furthermore, participants will be asked to give permission to contact their general practitioner (GP) for previous serologic examination(s) to exclude coeliac disease (e.g. anti-tTG IgA test or upper GI endoscopy). Serological tests (i.e. anti-tTG IgA) to rule out coeliac disease will be carried out during a visit prior to the screening visit, if tests to exclude coeliac disease have not been done before and if participants still consume traces or very low amount of gluten (as defined by the Biagi questionnaire) in their current diet. Volunteers will only be eligible when coeliac disease is sufficiently ruled out by means of serologic tests and if they meet the in/exclusion criteria. The blood sample (via venepuncture) for anti-tTG IgA will be taken prior to the screening visit and the results can take up to approximately 7 days. In the exceptional case of a positive test, the participant cannot participate in this study and their GP will be informed (see also IC form). To prevent us from collecting additional data from a non-eligible participant, it is preferred to have the test results available before the screening visit.

The screening visit will require approximately 60 minutes and will take place at the MUMC+, Amsterdam UMC or WUR, The Netherlands. The serological test visit requires an additional visit of 20 minutes.

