3.2 Test day (Day 1)

On the test day, upon arrival in MUMC+, Amsterdam UMC or WUR, the participants will be informed by the researcher(s) that they have been allocated to a specific group (*i.e.* E+ or E-). They will then receive either gluten-containing (G+) or gluten-free (G-) oat bread. The participant and the investigator will both be blind to the actual study intervention the participant will receive, *i.e.* the gluten-containing (G+) or gluten-free bread (G-) within each of the expectancy groups (See Figure 2).

This randomization results in 4 groups:

Group 1: Participants with the expectation of receiving gluten-free bread but actually receiving gluten-containing bread during the test day (E-, G+).

Group 2: Participants with the expectation of receiving gluten-free bread and actually receiving gluten-free bread during the test day (E-, G-).

Group 3: Participants with the expectation of receiving gluten-containing bread and actually receiving gluten-containing bread during the test day (E+, G+).

Group 4: Participants with the expectation of receiving gluten-containing bread but actually receiving gluten-free bread during the test day (E+, G-).

During the test day, participants are asked to come to the MUMC+, Amsterdam UMC or WUR in a fasted state at 8.00AM. Before the participants are informed about which group they are assigned to, they will first have to fill in the symptom questionnaire and the positive and negative affective scale (PANAS) as baseline measurements. Then (± 8.15 AM) they will be informed that they have been allocated to the gluten-containing or gluten–free groups (i.e. creating expectancy, E- or E+) and at 8.30AM they have to consume 2 slices of study bread for breakfast and at 12.30PM a further 2 slices for lunch. All slices can be prepared with margarine plus cooked ham, or cheese, or marmalade (one standardised portion of one topping per slice, all gluten-free). Furthermore, they will be allowed to drink coffee, tea or water (ad libitum) during the test day. Other foods or drinks are not permitted during the test day until 4.30PM. During the test day, the participants are free to do what they want to (watching TV, reading, working, possibly take a walk), provided that they complete the questionnaires every hour.

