Frozen packages of bread portions for the test day will be provided by European Bakery Innovation Centre, Papendrecht, The Netherlands, with a label that refers to the "expectancy" arm, but the actual treatment is blinded. Participants will be asked to report their GI symptoms, extra-intestinal symptoms, stool characteristics, and the PANAS in an electronic diary at baseline (at 8.00AM) and every hour till 4.30PM. After 4.30PM, participants will go home and will be allowed to eat freely as normal. During the study visits and telephonic contacts, the presence of serious adverse events will be checked. Participants will also be instructed to contact the researcher if their health status changes.

If participants are unable to stay at the MUMC+, Amsterdam UMC or WUR the entire day, they will receive the breakfast and the baseline questionnaire at the study location and can do the follow-up (*i.e.* completing the hourly questionnaire and consuming the study lunch) at home or at work, provided that all hourly questionnaires will be completed on the same tablet or notebook. If necessary, a study tablet will be provided for the test day. Subjects will receive a text message 5 minutes before each timepoint they have to fill in a questionnaire and will be informed that time of completion will be logged. Furthermore, participants have to adhere to the dietary restrictions. If possible, participants consume the study lunch in the presence of the researcher. Alternatively, participants are asked to provide pictures as proof of completely consuming the study lunch. The starting time of the test day can be flexible (before 9.00AM) and results in a shift of all time points, therefore it does not affect the structure of the test day. Any alterations in the test day (e.g. location of completing the hourly questionnaires) will be logged and taken into account during analyses.

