7.1.2 Secondary study parameters/endpoints

- Abdominal pain

- Abdominal discomfort

- Belching

- Bloating

- Flatulence

- Diarrhoea

- Constipation

- Urge to empty bowel

- Fullness

- Nausea

- Tiredness

- Headache

- Foggy Mind

Intestinal symptoms, measured on 100-mm VAS.

(See "F2_Klachtendagboek_WoWstudy_

Versie1.0_05-03-2018")

Extra-intestinal symptoms, measured on 100-mm

VAS. (See "F2_Klachtendagboek_WoWstudy_

Versie1.0 05-03-2018")

- Average stool frequency and consistency (measured by the Bristol Stool Scale)

- Changes in mood measured by PANAS (e.g. interested, alert, excited and distressed, ashamed, nervous).

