Participants will be asked to rate their daily symptoms on 100-mm VAS scale as well as rating their stool pattern during each hour (only after bowel movement) at the test day and at the end of day 1, 2, 3. The diary includes six sections: 1. Stool frequency and consistency - Bristol Stool Scale, 2. GI Symptoms, 3. Overall GI symptoms, 4. Other symptoms, 5. What did you eat today?, 6. Medication. The questionnaire can be completed at the MUMC+ or at home (or work), provided that the same tool is used to complete all the hourly questionnaires.

Blood sampling to exclude coeliac disease

Serological tests (*i.e.* anti-tTG) to rule out coeliac disease will be carried out during screening, if tests to exclude coeliac have not been done before and if participants still consume traces or very low amounts of gluten in their current diet (according to the Biagi questionnaire). This is estimated to be in about 20% of the participants who indicate interests to participate in the study. In this subgroup of participants, a venepuncture (10mL blood sample) will be done to exclude coeliac disease by means of serological tests on anti-tTG IgA. Blood samples will be collected from an antecubital vein in the fore-arm. This his may lead to minor discomfort and can cause small and transitory hematoma/bruises to appear.

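### The Summary promises average stool frequency and consistency before as well as after the bread, but the scheduled diary holds only one pre-bread entry, on the test morning

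*Protocol*

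**What the plan says.** The Protocol Summary, under main study parameters, says: "Average stool frequency and consistency will be measured by the Bristol Stool Scale (BSS) before and after intervention". Section 7.1.2 lists the same item among the secondary endpoints as "Average stool frequency and consistency (measured by the Bristol Stool Scale"), without mentioning a before-and-after measurement.

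The recording schedule is spread over several sections:

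- Section 3.2 has participants report symptoms, "stool characteristics, and the PANAS in an electronic diary at baseline (at 8.00AM) and every hour till 4.30PM". Before they learn their group, "they will first have to fill in the symptom questionnaire and the positive and negative affective scale (PANAS) as baseline measurements".
- Section 7.3 describes the diary as rating daily symptoms and "rating their stool pattern during each hour (only after bowel movement) at the test day and at the end of day 1, 2, 3".
- The list of study elements in Section 3 gives "Follow-up questionnaires End of day 1, day 2 and 3". No end-of-day form is listed for any day before the test day.
- Section 3.1 sets an eligibility rule: "Participants must have an overall symptom score for gastro-intestinal symptoms below or equal to 30mm in VAS-score over the last week".
- Section 3 gives the purpose of the later days: "a follow-up period of 2 days is included to monitor the effects of the 1-day bread intervention and the disappearance of the symptoms".

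**The concern.** An average frequency needs a count over a period of days. The schedule offers a single moment on the test morning, with the participant fasted, about 15 minutes before the expectancy message and 30 minutes before the bread. The entry concerns stool only if there has been a bowel movement. The before value promised in the Summary is therefore missing for frequency, and present for consistency only in a subset selected by chance and by bowel habit.

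What is at stake is a within-person change in a named secondary endpoint. A later analysis plan can choose how to analyse stool data, but it cannot recover a pre-intervention record that was never collected. If the baseline-versus-after model of Section 9.1 is applied to stool, it needs both values from each participant, and many would lack the first.

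A smaller, related weakness affects the evening symptom ratings. They cover a whole day, whereas the 8.00AM score describes a moment at the start of one. The two do not share a recall window.

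**Working it through.** The plan gives no figure on this point, so there is nothing to reproduce. The check sets the schedule against the promise and then adds an illustration.

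**Step 1: count the scheduled records (Sections 3, 3.2, 3.3 and 7.3).**

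| Record | Before the bread | After the bread |
|---|---|---|
| Test-day diary entry | 1 (8.00AM) | hourly to 4.30PM |
| End-of-day form | 0 | 3 (days 1, 2, 3) |

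Section 3 puts the whole study at 3 days after inclusion, which leaves no scheduled diary day ahead of the test day.

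**Step 2: what the one early entry can yield.** Frequency is a count per unit of time, and one entry does not give an average over days. Consistency needs a stool, and Section 7.3 makes the rating conditional on one.

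**Step 3: how many participants might have a stool to rate.** None of the inputs here is a document figure, except the group size of 20 from Section 4.4. Assume stools arrive at a constant rate λ per day over 16 waking hours, and that the 8.00AM entry covers w hours. Then P(at least one stool) = 1 − exp(−λw/16).

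| λ (per day) | w (h) | λw/16 | P | Expected of 20 |
|---|---|---|---|---|
| 0.5 | 0.25 | 0.0078 | 0.8% | 0.16 |
| 1 | 0.25 | 0.0156 | 1.6% | 0.31 |
| 1 | 1 | 0.0625 | 6.1% | 1.21 |
| 3 | 1 | 0.1875 | 17.1% | 3.42 |

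Bowel movements tend to cluster in the morning, and the form might look back further than an hour, so the true share could be higher. Neither possibility turns one entry into an average frequency comparable with the daily records of days 1 to 3.

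**Step 4: what a proper baseline could gain in precision.** Adjusting for a baseline that correlates r with the outcome multiplies the residual variance by 1 − r², a cut of r². The documents give no r, so only a range can be shown:

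- r = 0.3: 0.09, a 9% cut
- r = 0.4: 0.16, a 16% cut
- r = 0.6: 0.36, a 36% cut
- r = 0.8: 0.64, a 64% cut

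**Step 5: references available for the evening symptom scores.** There are two. The 8.00AM questionnaire covers all symptoms but is momentary. The screening score covers a whole week on the diet, but the protocol describes it for overall GI symptoms only, and it is also the eligibility cut-off. Neither matches an end-of-day rating. The three evening forms do match one another.

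**The case against.** The other side has several fair points.

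- **Something is recorded beforehand.** A reader might infer that no stool or symptom data exist before the intervention. That is not so: Section 3.2 schedules stool characteristics, symptoms and mood at 8.00AM, ahead of both the message and the bread. This stands. It limits the point to what one conditional entry can provide.
- **Disappearance of symptoms.** A reader might also infer that days 2 and 3 cannot show symptoms fading. The documents do not support this. The evening scores of days 1, 2 and 3 use the same form at the same time of day, so a decline can be described. The 8.00AM score and the last-week screening score give reference levels. If evenings are generally worse, the shift is common to all four randomised groups and cancels between them. Only the mismatch in recall windows remains.
- **Post-intervention comparison.** Randomised arms can be compared on stool outcomes without a baseline, and Section 7.1.2 already words the endpoint without one. This stands, and it is why a rewording is an acceptable alternative.
- **Section 9.1 does not name stool.** Its list is open-ended, so the repeated-measures model may not be meant for this endpoint. This stands, and no claim of a broken model is made.
- **Unseen forms.** The diary form, the screening questionnaire and the Rome form are not reproduced. A usual-stool-pattern item or a longer look-back cannot be ruled out. This lowers certainty about the 8.00AM entry, but a recalled usual pattern would not be a diary record comparable with days 1 to 3.

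**Conclusion.** The point holds for the stool endpoint. The Summary's before-and-after measurement and the diary schedule do not agree. The scheduled diary gives no average pre-intervention stool frequency, and gives pre-intervention consistency for only some participants. Under the assumptions shown that is roughly 1% to 17% of them, and possibly more if stools cluster in the morning or the form looks back further.

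For symptoms the weakness is lesser: there is no like-for-like reference for the end-of-day ratings. It does not follow that the stool endpoint cannot be analysed or that disappearance cannot be assessed.

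No fixed gain in precision should be claimed, because r is unknown and the cut runs from 9% to 64% over r = 0.3 to 0.8. The primary outcome, overall GI symptoms within 8 hours, is untouched. This is an inexpensive improvement to a secondary endpoint, and it rests on the schedule as written and not on the illustration.

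**What to change.** Have participants complete the existing end-of-day diary (symptom scales and Bristol Stool Scale) on 2 to 3 evenings directly before the test day, while they are on the diet that Section 4.2 already requires. Use the mean of those evenings as the baseline for stool frequency and consistency, and as the like-for-like reference for the end-of-day symptom scores of days 1 to 3. Keep the 8.00AM score as the baseline for the hourly outcomes.

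The cost is about 5 minutes per evening, which is the Summary's own estimate for the daily form, so 10 to 15 minutes per participant, plus a short amendment. No visit is added. Participants already fill in the GAD-7, PHQ-9 and PHQ-15 electronically at home between screening and the test day (Section 7.3). The extra entries precede the expectancy message, so they leave blinding and treatment as they are.

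If this is not adopted, restate the stool endpoint in the Summary as a post-intervention comparison between the randomised arms, in line with Section 7.1.2. That costs one sentence.
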